Treatment options ranges from conservative, which consist of non-invasive such as rehabilitation to more invasive injection procedure and finally, surgical treatment. A systematic review showed limited evidence that surgery is more effective in treating rotator cuff tear than conservative treatment alone⁷. At an early stage, the use of anti-inflammatory, exercise and electrotherapeutic modalities are to control the inflammatory phase of tendon disease. However, despite the treatment above, recalcitrant tendinopathy may manifest because, once damaged, the biological and biomechanical properties of tendon tissue never completely restored. Healing times in chronic tendinopathies are prolonged as tendons are relatively less vascular and local blood flow is less than verged delivered to the muscles. Thus, in recent years, the use of platelet rich plasma and prolotherapy has been emerging as a treatment option for rotator cuff tendinopathy⁸. Platelet rich plasma with its supraphysiologic platelet concentration has the potential to release biologically active proteins that promote cellular recruitment, growth and morphogenesis. Tendon healing is thought to be stimulated via enhanced fibroblast migration and proliferation, increased the tissue vascularization and collagen deposition⁹.

Prolotherapy is an injection of small volumes of an irritant such as dextrose into the insertion sites of the damaged tendon, which promotes the growth of normal tissue. Studies hypothesize that the injected substance mimics the natural healing processes by facilitating a

local inflammatory cascade, which triggers the release of growth factors and collagen deposition¹⁰. Both interventions showed a good outcome for the treatment of rotator cuff tendinopathy.

Hypothesis:

1. Participants treated with prolotherapy injection showed a significantly higher clinical and functional scores compared to control group
2. Participants treated with platelet-rich plasma injection showed a significantly higher clinical and function scores compared to control group

Problem statements:

Platelet rich plasma and prolotherapy have been the option treatment for tendinopathy, particularly in lateral epicondylitis and Achilles tendinosis. However, the study on the rotator cuff is still limited. No study compares the effect of PRP to prolotherapy is available. Furthermore, the reviews on the factors that may influence the outcome were minimal.

Literature Review

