- 4) Patient with the following laboratory findings: Haemoglobin level less than 10 g/L and/or platelet count less than 100,000/ μ L
- 5) Unable to follow study protocol

Sample size calculation and estimation

The sample size was estimated based on the primary outcome of functional score. Improvement was defined by a decrease in the mean Shoulder Pain and Disability Index (SPADI) of 17.7 ± 3.7 in the platelet-rich plasma group¹¹ and 16.12 ± 12.82 ¹¹ for prolotherapy. For this study, the sample size was calculated after taking into account the desired statistical significance level set at 5%, and the power of the study set at 80%, with type I error rate of less than 0.05 is permitted and a false-negative rate of less than 0.20. The sample size is calculated using the G*Power version 3.1.9.2 software¹¹. With the assumption of 30% drop out, hence, to detect a difference in the functional outcome, a minimum of 30 patients in each group is required.

Procedures

Informed consent will be obtained from the patients before intervention. All participants are required to complete the functional questionnaire (name of the functional questionnaire = SPADI??). Participants will be assessed by Sports Physician for eligibility. Subsequently, ultrasound assessment will be performed by one musculoskeletal (MSK) radiologist or a Sports Physician with more than 10 years' experience in performing MSK ultrasound. Blood will be sent for full blood count test to assess the hemoglobin and platelet levels. A plain shoulder radiography (indicate views that will be ordered) will also be

performed to exclude Type III acromion. Electromyogram and strength testing will be done at the first visit for all patients.

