Patients who fulfilled the study criteria will be randomly assigned using computer-generated block randomization to receive either PRP, prolotherapy or normal saline injections. On the procedure day, blood will be withdrawn from all the patients to ensure blinding of participants. A covered syringe contains the solutions will be prepared by the investigator to ensure its content is not visible. The procedure will be performed under ultrasound guidance with the patient sitting on a chair, in a modified crass position. All shoulder injection will be performed by a co-investigator who are not involved in outcome measure assessment of patient's progress. Post injection, the patients will be advised to rest, and avoid vigorous shoulder activities. The patients are allowed to take paracetamol if the pain is intolerable (up to 1000mg every 6 hourly. Patient are required to record the amount of paracetamol that they take.

During the follow up, the Sports Physician and or radiologist who assess the patient at baseline will repeat the assessment. The involved physician will not be informed of the intervention received by the participants. (Refer to Figure 1: Flowchart of the study).

Intervention

Platelet rich plasma: We will use a commercially available kit (YCELLBIO Kit). The autologous PRP will be prepared in accordance with the manufacturer's guideline. Fifteen (15) ml blood will be collected, according to a standard PRP kit; this volume can produce approximately 3 mL of PRP. Two milliliters of the PRP will be delivered to the injured area under ultrasound guidance.

Prolotherapy: We will dilute dextrose 50% in bacteriostatic water to get 16.5 % solution. One to two ml of the dextrose solution will be injected into the area of painful tendinosis under ultrasound guidance.

All participants will receive single injection. The injection will be under ultrasound guided intralesional.

Outcome measures

Study assessments will include the following assessment at baseline, 3 weeks, 3 months and 6 months.

- Clinical outcome: Range of movement and special test for rotator cuff
- Functional outcome: Shoulder Pain and Disability Index (SPADI) questionnaire
- Pain: Visual analogue score (VAS)
- Ultrasound assessment characteristics: tendon thickening, changes in the normal contour and echotexture lost in the fibrillar pattern, hypoechoic changes, swelling, neovascularization, and partial tear.

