- Biomechanics analysis: dynamometer for strength and electromyogram of periscapular muscle

Statistical Analysis

The primary outcome of the study which consist of the mean difference in pain and shoulder function will be analyzed with independent T-test. For secondary outcome, range of movement, strength, ultrasound findings and electromyogram result independent T-test will be used for continuous data and Fisher exact test for categorical data.

D) Expected Results/Benefit

i. Novel theories/New findings/Knowledge

Platelet rich plasma and prolotherapy is a treatment of choice for recalcitrant supraspinatus tendinopathy. However, the effect may be influenced by several factors such as clinical examination at presentation and ultrasound findings.

ii. Specific or Potential Applications:

PRP and prolotherapy can result in improvement of shoulder function in patients with chronic shoulder pain. The costs are cheaper compared to surgery.

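### The t-tests make no adjustment for baseline scores the trial already collects; pairwise ANCOVA would usually be more precise, by an amount set mainly by a correlation the plan does not give

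*Combined protocol and SAP*

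**What the plan says.** Under Statistical Analysis, the primary analysis is one clause: the "mean difference in pain and shoulder function will be analyzed with independent T-test". For the secondary outcomes, which include range of movement and strength, "independent T-test will be used for continuous data and Fisher exact test for categorical data". No covariate, regression or ANCOVA appears there or anywhere else in the document.

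The baseline values will exist. Outcome measures states: "Study assessments will include the following assessment at baseline, 3 weeks, 3 months and 6 months". The list that follows covers range of movement, SPADI, VAS and dynamometer strength. Procedures adds: "Electromyogram and strength testing will be done at the first visit for all patients".

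Whether the t-test compares follow-up scores or changes from baseline is not stated. The only hint is in the sample size section: "Improvement was defined by a decrease in the mean Shoulder Pain and Disability Index (SPADI", with a value of "17.7 ± 3.7 in the platelet-rich plasma group" and 16.12 ± 12.82 for prolotherapy. A decrease is a change from baseline, so change is the likelier reading for SPADI. For range of movement and strength there is no hint either way.

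**The concern.** A patient's score before treatment usually predicts the score after it. A t-test on follow-up scores leaves that predictable part in the error term. A t-test on change scores removes some of it, but it subtracts the whole baseline (weight 1) whatever the actual relation is. ANCOVA estimates the weight from the data. It also reduces the error tied to whatever baseline imbalance chance produces, which can be noticeable in arms this small.

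Precision is at stake. The sample size section plans 30 per arm "With the assumption of 30% drop out", so about 21 per arm are expected to complete. The hypotheses compare each active arm with control (for example, "Participants treated with prolotherapy injection showed a significantly higher clinical and functional scores compared to control group"), and a further objective compares the two active arms. Each comparison therefore rests on about 42 patients.

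**Working it through.** **The plan's own figure.** The plan gives 30 per group (5% level, 80% power, 30% dropout). I could not reproduce it from the two stated decreases. Reading ± as SD:
- difference 17.7 − 16.12 = 1.58
- common SD √((3.7² + 12.82²)/2) = 9.435
- two-sided n = 2(1.96 + 0.84)² × 9.435²/1.58² ≈ 560 per arm, or 560/0.7 = 800 with dropout.

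This matters here only as a limit on what adjustment can do. If 9.435 is a change-score SD, the large-sample ANCOVA factor (1 + r)/2 gives 560 × 0.65 = 364 at r = 0.3 and 560 × 0.85 = 476 at r = 0.7.

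**Inputs for the precision check.**
- Completers: 30 × 0.7 = 21 per arm, so N = 42 for a pair of arms.
- r, the baseline-to-follow-up correlation: not in the documents; assumed 0.3, 0.5, 0.7, 0.8, 0.9.
- SDs equal at both visits and in both arms: assumed, and relaxed below.

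**Formulas.** With the follow-up variance set to 1, a follow-up comparison has variance 1, a change-score comparison 2(1 − r), and ANCOVA 1 − r². Estimating the slope costs a factor of 1 + 1/(42 − 4) = 1.026. Hence:
- ANCOVA against change scores: 1.026 × (1 + r)/2
- ANCOVA against follow-up scores: 1.026 × (1 − r²)
- CI width ratio: the square root of the factor with ordinary errors; about 1.04 times that with HC3, because simulation at 21 per arm shows HC3 intervals about 4% wider.

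Example at r = 0.5: 1.026 × 0.75 = 0.77 against either comparator. √0.77 = 0.877, so the CI is 12% narrower; 0.877 × 1.04 = 0.912, so with HC3 it is 9% narrower.

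| Assumed r | Variance vs change | Variance vs follow-up | CI vs change, ordinary | CI vs change, HC3 | CI vs follow-up, HC3 |
|---|---|---|---|---|---|
| 0.3 | 0.67 | 0.93 | 18% narrower | 15% narrower | no gain |
| 0.5 | 0.77 | 0.77 | 12% narrower | 9% narrower | 9% narrower |
| 0.7 | 0.87 | 0.52 | 7% narrower | 3% narrower | 25% narrower |
| 0.8 | 0.92 | 0.37 | 4% narrower | no gain | 37% narrower |
| 0.9 | 0.975 | 0.195 | 1% narrower | 3% wider | 54% narrower |

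Simulation with 40,000 trials per r agrees with these variances and widths.

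**Break-even.** With ordinary errors, ANCOVA gains against follow-up scores above r = √(1 − 1/1.026) ≈ 0.16, and against change scores below r = 2/1.026 − 1 ≈ 0.95. Judged by CI width with HC3, the limits tighten to just above 0.3 and about 0.8.

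**Unequal spread.** The ± values belong to decreases. If they are SDs, they are change-score SDs, and they differ by 12.82/3.7 ≈ 3.5-fold. With an SD of s at both visits, the implied correlation in an arm is 1 − SD²/(2s²), where SD is that arm's change-score SD. For an assumed s of 15 to 25 this is 0.97 to 0.99 for PRP and 0.64 to 0.87 for prolotherapy. The factor against change scores for that pair, using the mean of the two correlations, is then about 0.92 to 0.99, and the HC3 standard error is 0 to 3% larger than the t-test's. At s = 10 the correlations are 0.93 and 0.18 and the factor is about 0.80, so a gain returns.

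The gain can also shrink when r is low in one arm. With a slope of 0.5 in both arms and three times the residual SD in one, r in the noisier arm falls to 0.19. The standard errors are then 0.606 for ANCOVA, 0.617 for follow-up scores and 0.620 for change scores.

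**Why robust errors.** If residual SDs were 3.7 and 12.82 and completers 26 and 16 (or the reverse), ordinary pairwise ANCOVA at a nominal 5% rejects a true null in 11.7% (or 2.0%) of simulated trials, and HC3 in 5.2% (or 4.3%). The split of completers is assumed.

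**The case against.** The strongest reply is that the planned test is valid and the gain may be small. On the likelier reading for SPADI, baseline is already used by subtraction. If r is 0.8 or more, ANCOVA with HC3 errors then gives no narrower interval, and at 0.9 a slightly wider one. Against follow-up scores at r = 0.3, HC3 power for the 0.44 SD effect quoted in the literature review is 0.274, against 0.282 for the t-test. All of this stands, and it is why the benefit cannot be stated as one number or promised at every r.

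It does not remove the point. At r = 0.3 to 0.7 there is a gain over change scores even with HC3, and above r of about 0.3 there is a gain over follow-up scores that becomes large. Since the plan states neither r nor the comparator, ANCOVA is the safer choice: at every assumed r it is better than, or within a few per cent of, the better t-test.

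A reader might infer that the plan ignores its baseline data. The documents do not support that for SPADI, because the sample size section speaks of a decrease. What they support is that no adjustment is specified and that the scores compared are not stated.

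**Conclusion.** The point holds as one of efficiency. No baseline adjustment is planned for SPADI, VAS, range of movement or strength, although all four are measured at baseline, and the plan leaves open which scores the t-test compares. With 21 completers per arm, equal SDs and r between 0.3 and 0.9, ANCOVA removes about a third to 2.5% of the variance of a change-score comparison, or about 7% to 80% of that of a follow-up comparison. HC3 errors give back about 4% of CI width. The gain can be near zero if r is very high, or if it is low in one arm.

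Two stronger readings are not supported. The t-test is not biased: allocation is randomised, and the unadjusted difference is unbiased on average. Nor would ANCOVA rescue the sample size: on the plan's own decreases, hundreds of completers per arm would still be needed to compare PRP with prolotherapy. All gains rest on assumed values of r, and the unequal-spread argument rests on reading ± as SD, which the plan does not state.

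**What to change.** In Statistical Analysis, replace the t-tests for SPADI, VAS, range of movement and strength with ANCOVA fitted separately for each pairwise comparison of arms. The outcome is the score at one named scheduled follow-up visit, arm is the factor, and the patient's own baseline score is the covariate. Report adjusted mean differences with 95% confidence intervals.

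Use heteroscedasticity-robust (HC3) standard errors, because the quoted ± values, if SDs, suggest very different spread between arms. State the downside: at this size HC3 intervals are about 4% wider than ordinary ones. Keep the t-test as a supporting analysis, and say whether it compares follow-up or change scores.

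The cost is two or three sentences, including the name of the primary visit. No new data, visits or patients are needed.

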23. Cole B et al. Ultrasound-guided injections for supraspinatus tendinopathy: corticosteroid versus glucose prolotherapy - a randomized controlled clinical trial. *Shoulder Elbow*. 2018 Jul;10(3):170-178.
24. George J et al. Comparative Effectiveness of Ultrasound-Guided Intratendinous Prolotherapy Injection with Conventional Treatment to Treat Focal Supraspinatus Tendinosis. *Scientifica* Volume 2018, Article ID 4384159.
25. Lin MT et al. Comparative Effectiveness of Injection Therapies in Rotator Cuff Tendinopathy: A Systematic Review, Pairwise and Network Meta-analysis of Randomized Controlled Trials. *Arch Phys Med Rehabil*. 2018 Aug.

Appendix 1

SHOULDER PAIN AND DISABILITY INDEX (SPADI)

Please place a mark on the line that best represents your experience during the last week attributable to your shoulder problem.

Pain scale

How severe is your pain?

Circle the number that best describes your pain where: 0 = no pain and 10 = the worst pain imaginable.

At its worst?	0	1	2	3	4	5	6	7	8	9	10
When lying on the involved side?	0	1	2	3	4	5	6	7	8	9	10
Reaching for something on a high shelf?	0	1	2	3	4	5	6	7	8	9	10
Touching the back of your neck?	0	1	2	3	4	5	6	7	8	9	10
Pushing with the involved arm?	0	1	2	3	4	5	6	7	8	9	10

Disability scale

How much difficulty do you have?

Circle the number that best describes your experience where: 0 = no difficulty and 10 = so difficult it requires help.

Washing your hair?	0	1	2	3	4	5	6	7	8	9	10
Washing your back?	0	1	2	3	4	5	6	7	8	9	10
Putting on an undershirt or jumper?	0	1	2	3	4	5	6	7	8	9	10
Putting on a shirt that buttons down the front?	0	1	2	3	4	5	6	7	8	9	10
Putting on your pants?	0	1	2	3	4	5	6	7	8	9	10
Placing an object on a high shelf?	0	1	2	3	4	5	6	7	8	9	10
Carrying a heavy object of 10 pounds (4.5 kilograms)	0	1	2	3	4	5	6	7	8	9	10
Removing something from your back pocket?	0	1	2	3	4	5	6	7	8	9	10

Appendix 2

PATIENT'S FORM

Patients' History

Name:

RN:

Age:

Gender: Male/ Female

Ethnics: Malay/ Chinese/ Indian/ Others _____

Occupation:

Job description:

Smoker: No / Yes

Medical Illness: No/ Yes

Medication:

Clinical Examination

Height:

Weight:

BMI:

Dominant Hand: Right/ Left

Involved Side: Right/ Left/ Bilateral

Range of movement (goniometer):

ROM	Degrees	ROM	Degrees
Forward flexion		Internal Rotation (hand at side)	
Extension		Internal rotation (90)	
Abduction		External rotation (hand at side)	
Adduction		External Rotation (90)	

Painful site (most tender area)

Non-specific anterior		Supraspinatus fossa	
Non-specific posterior		AC joint	
Greater tuberosity		Others:	
Bicipital groove			

Special Test:

		Description
Empty can (Jobe's test)	+ / - / NA	
Full can test		
Resisted external		
Gerber's lift off test		
Hawkin's Kennedy		
Neer's Sign		
Drop arm test		
Other test with positive findings:		

Handheld (Commander dynamometer test)

	T1	T2	T3	Avg		T1	T2	T3	Avg
Forward flexion					Internal Rotation (hand at side)				
Abduction					Internal rotation (90°)				
Abduction 30°					External rotation (hand at side)				
Adduction					External Rotation (90°)				

*T- Trial

Avg- Average
